6 OUTCOMES

6.1 Primary outcomes

The primary outcome consists of the quality of the medicines' pathway in participating NHs, represented by overall performance scores, measured at the end of the study (i.e. 1 year).

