7.4 Data analysis

7.4.1 Primary objective: effectiveness of different formats and intensities of support

The primary outcome measure consists of the overall performance score with regard to the medicines' pathway in participating NHs. This overall performance score will be calculated at baseline (i.e. before) and at the end of the study (i.e. after), and will be calculated on data collected with the quick scan, in particular the performance assessment. The importance assessment will thus not be used to determine the primary outcome.

For data analysis, responses collected through the performance assessment will be dichotomized. Responses 'Absolutely so' and 'Rather so' will be considered as 'key activity implemented (i.e. scored 1). The other response options ('A little', 'Rather not', 'Absolutely not') will be scored 0 and thus considered as 'not implemented'. For each respondent, a performance score will be calculated by determining the proportion of KAs considered as 'implemented'.

A before-after comparison of the overall performance scores will be executed by means of a linear, mixed model with random effects of NH and respondent (most respondents will be involved in before and after setting) and fixed effects of track, time (before/after), the interaction between track and time, type of respondent (coordinating physician, nurse, pharmacist, etc.), the NH's membership of a professional association and the number of beds available. Note that the focus of interest is the interaction between track and time. From the model, least-squares means (with 95% confidence intervals) and changes in means will be reported. If required, a transformation of the performance score will be considered to obtain a more symmetric distribution of the model residuals.

The changes of the activity-specific performance will be evaluated for each KA separately using a generalized linear mixed model (i.e. a logistic regression model with random effects of NH and respondent) with the same fixed effects as in the linear mixed model.

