8 STUDY POPULATION AND RECRUITMENT

A pilot study will be performed first, in approximately five to ten NHs. The project call (see Appendix 10 and 11) for this phase is planned to be launched in February 2024 but will not occur before receiving

approval of the Ethics Committee. A call for the actual cluster RCT, which will include approximately 100 NHs, is scheduled to be launched in March 2024. As the sample size of 100 NHs has been determined and defined in the Decision of the Flemish Government, no sample size calculation has been performed.

Project calls for NHs will be distributed by Departement Zorg (Flemish Government) and umbrella organizations (i.e. VLOZO, VVSG and Zorgnet-Icuro). In addition to this, a dedicated call will be targeted at NHs that contacted the research team during the last year with regard to the lifelong learning course 'Coordinating pharmacist in nursing homes' or to request access to materials and tools developed during earlier research projects (e.g. Come-On study, RESPECT project).

Nursing homes who are interested to participate will be asked to register through an online application form that will be made available in Qualtrics (see Appendix 12). In this application form, NHs will be asked to formulate a motivation for participation, to indicate the willingness of the coordinating physician to participate, to make a proposal for the composition of their local project team, to suggest who will be the local project coordinator, etc.

Recruitment of NHs will occur in two stages. First, if more than 100 NHs apply, a set of 100 NHs will be drawn at random from the pool of NHs who have expressed their interest to participate in the study. This sampling, if performed, will take into account the NH's membership to a professional association, meaning that the selection of NHs will occur proportionally to the real-life distribution of NH memberships in Flanders (i.e. no membership, Zorgnet-Icuro, VVSG, and VLOZO).

The sample of 100 will be randomised into the different tracks (cfr. supra), stratified on membership to a professional association, initial performance score and number of beds. Since these characteristics of all participating centres are known at the start of the study, a list can be created with all possible randomisations safeguarding the required balance in characteristics. From this list of acceptable randomisations, one will be drawn at random.

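### The primary model gives each track its own baseline mean although allocation is balanced on the baseline score, so standard errors are overstated and the track-by-time test is conservative

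*Protocol*

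**What the plan says.** **Primary model (Protocol 7.4.1).** Before and after overall performance scores are both outcomes in a "linear, mixed model with random effects of NH and respondent". The fixed effects include "fixed effects of track, time (before/after), the interaction between track and time", plus respondent type, association membership and number of beds. The treatment effect is named: "Note that the focus of interest is the interaction between track and time". Least-squares means and changes in means are to be reported. On repeat respondents the section says only that "most respondents will be involved in before and after setting".

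**Allocation (Protocol 8).** NHs are randomised "stratified on membership to a professional association, initial performance score and number of beds". The reason given is: "Since these characteristics of all participating centres are known at the start of the study". From them "a list can be created with all possible randomisations safeguarding the required balance in characteristics", and one allocation is drawn from that list.

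**Sample size (Protocol 8).** About 100 NHs, a number set outside the study, with no sample size calculation. The protocol gives no SD, ICC, before-after correlation, number of respondents for the analysis, or allocation ratio.

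**The concern.** A track main effect lets the four baseline means differ freely, so the track-by-time term compares before-after changes. That parametrisation suits groups that may truly differ at baseline. Here they do not differ in expectation, and the allocation actively balances them on the NH's initial score.

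Of the three balancing factors, membership and beds enter as covariates. The initial score, plausibly the most prognostic, enters only as the before outcome with unconstrained track means. The model therefore charges the treatment contrast with baseline sampling variation that the design has largely removed.

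What is at stake is the width of the reported intervals and the power of the primary comparison. The number of NHs is fixed, so the analysis is one of the few remaining ways to gain precision. The choice also carries over: 7.4.1 uses the same fixed effects for the activity-specific models and the same approach for the process-specific scores.

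**Working it through.** The protocol states no power or precision figure, so there is none to reproduce.

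**Inputs.** From the protocol: four tracks, about 100 NHs, random effects of NH and respondent. Assumed: 25 NHs per track, two-sided 5% level, and the correlation rho between an NH's mean score before and after, shown over a range.

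**Step 1: model-based variance.** Scale NH means to variance 1.
- Planned interaction: variance of a change = 1 + 1 − 2rho = 2(1−rho).
- Common baseline mean, or adjustment for baseline: residual variance of follow-up given baseline = 1−rho².
- Ratio: (1−rho)(1+rho) / [2(1−rho)] = (1+rho)/2, below 1 for every rho below 1.

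| rho | 2(1−rho) | 1−rho² | variance ratio | SE ratio |
|---|---|---|---|---|
| 0.3 | 1.40 | 0.91 | 0.65 | 0.806 |
| 0.5 | 1.00 | 0.75 | 0.75 | 0.866 |
| 0.7 | 0.60 | 0.51 | 0.85 | 0.922 |
| 0.9 | 0.20 | 0.19 | 0.95 | 0.975 |

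**Step 2: respondent level.** Change scores are exact only when everyone answers twice. Generalised least squares was therefore run on individual responses, comparing eight free track-by-time means with one common baseline mean plus four follow-up means. Assumed ranges: 5 to 15 respondents per NH, 50% to 100% repeaters, NH share of variance 0.05 to 0.20, with and without an NH-by-time component. The variance ratio was 0.70 to 0.95 (SE 3% to 17% smaller). With 8 respondents, 75% repeaters and an NH share of 0.10 it was 0.83. Adding an NH-by-time share of 0.05 made it 0.77.

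**Step 3: what happens when allocation is balanced.** In 4,000 simulated trials per correlation, 100 NHs were allocated in blocks of four matched on baseline. The unit is the SD of an NH mean.

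| rho | analysis | true SD of estimate | mean model SE | type I error at nominal 5% |
|---|---|---|---|---|
| 0.5 | track × time | 0.247 | 0.283 | 2.8% |
| 0.5 | baseline-adjusted | 0.246 | 0.244 | 5.0% |
| 0.7 | track × time | 0.203 | 0.219 | 3.8% |
| 0.7 | baseline-adjusted | 0.203 | 0.202 | 5.2% |

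This agrees with step 1: at rho 0.5, √(2/25 × 1.00) = 0.283 and √(2/25 × 0.75) = 0.245. The estimates vary equally in truth. Only the planned model's SE is too large.

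**Step 4: power at rho 0.5.** Take the effect for which the planned model nominally has 80% power: (1.960 + 0.842) × 0.2828 = 0.792.
- Planned: (0.792 − 1.96 × 0.283) / 0.247 = 0.96, power about 83%.
- Baseline-adjusted: (0.792 − 1.96 × 0.244) / 0.246 = 1.28, power about 90%.

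**The case against.** **The planned model is not wrong.** A track, time and track-by-time mixed model is a common, unbiased analysis of a pre-post cluster trial. This stands: the point is a gain in efficiency, not the correction of an error. Nor is the baseline score ignored, since it is modelled jointly through the random effects.

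**The size is unknown.** This also stands. Every variance input is assumed, and at rho 0.9 the variance gain is only 5%.

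**Pre-allocation timing is inferred.** The protocol gives no timeline and does not say that the initial performance score is the same quick-scan score as the before outcome. A score used to balance the allocation must exist beforehand, so the inference is firm. But if some before responses came in after allocation, forcing equal baseline means could introduce bias that the planned model avoids. The fix therefore carries a condition.

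**Two stronger readings are tempting, and the documents support neither.**
- A reader might turn the variance ratio into NHs, for example 100/0.75 = 133 at rho 0.5, and infer that the planned estimate is that much noisier. That would apply to allocation not balanced on baseline. Under the balance section 8 provides, both estimators have nearly the same true sampling SD (step 3).
- A reader might see a conflict with section 6.1, which defines the outcome as quality "represented by overall performance scores, measured at the end of the study (i.e. 1 year"). There is none of substance: 7.4.1 reports least-squares means as well as changes, and under randomisation the difference in change and the 1-year difference target the same effect.

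**Conclusion.** The point holds as a matter of efficiency. The planned analysis is valid and unbiased but does not credit the baseline balance that the randomisation creates, so its standard errors are too large and its test conservative. The model-based variance ratio is (1+rho)/2: about 0.75 at rho 0.5, 0.85 at 0.7 and 0.95 at 0.9. At rho 0.5, with 25 NHs per track and tight balance, type I error falls to 2.8%, and power is about 83% where baseline adjustment gives about 90%.

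These figures rest on assumed correlations, equal tracks and tight balance; section 8 states no tolerance. With looser balance, part of the loss becomes a real loss of precision. They also assume that the random effects are right. The planned model has no NH-by-time term, and if NHs drift differently over the year, that omission makes standard errors too small. *Conservative* therefore describes the baseline parametrisation alone. For the logistic activity-level models the direction should carry over, but the formula is not exact.

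**What to change.** In Protocol 7.4.1:
- State that the before quick scan is completed in every NH before allocation, and that the initial performance score used in section 8 comes from it. The next change depends on this.
- Drop the track main effect. Keep one common baseline mean, time, and track effects at follow-up only, with the other covariates as planned. This retains respondents who answer only once. Alternatively, model the follow-up score with the NH's initial performance score as a covariate, which brings the third balancing factor into the adjustment.
- Add an NH-by-time random effect, so that the smaller standard errors are correctly calibrated.
- Report adjusted between-track differences at 1 year with 95% confidence intervals.
- Carry the same baseline constraint into the process-specific and activity-specific models.

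The cost is analysis wording only, with no new data and no change to the conduct of the trial. The change should be fixed before follow-up scores are seen.

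### Membership and number of beds enter the primary model only as main effects, so the track-by-time contrast is not adjusted for these two randomisation factors

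*Protocol*

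**What the plan says.** Section 8 of the protocol describes a constrained randomisation of the homes, "stratified on membership to a professional association, initial performance score and number of beds". One allocation is drawn from a list described as follows: "a list can be created with all possible randomisations safeguarding the required balance in characteristics".

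Section 7.4.1 specifies the primary analysis as a "linear, mixed model with random effects of NH and respondent (most respondents will be involved in before and after setting"), with "fixed effects of track, time (before/after), the interaction between track and time, type of respondent" and then, in the text that also names the track-by-time focus, "the NH's membership of a professional association and the number of beds available. Note that the focus of interest is the interaction between track and" … Track by time is the only interaction named, and no home-by-time random effect is named. The plan will report least-squares means with confidence intervals and changes in means.

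The models for single key activities are logistic mixed models "with the same fixed effects as in the linear mixed model". Process-specific scores follow the approach used for the overall score. The footnote in section 7.4.1 offers an alternative model with an effect of respondent within timepoint, but it has no home-by-time effect either.

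**The concern.** Two of the three factors that govern the allocation reappear in the primary model, so a reader will take the track comparison to be adjusted for them. It is not. Each factor enters as a single term that shifts a home's before and after scores by the same amount, while the parameter of interest compares changes.

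If membership or size predicts how much a home improves, two things follow. Any imbalance that the allocation left in these factors is not corrected in the tested effect, and the variation in change that they explain stays unexplained. The protocol states its list of fixed effects explicitly, so this is a stated choice and not a detail left to a later analysis plan.

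**Working it through.** **Inputs from the protocol.** Fixed and random effects as listed in section 7.4.1; randomisation factors and about 100 homes from section 8 ("A call for the actual cluster RCT, which will include approximately 100 NHs, is scheduled to be launched in March 2024"); four tracks. No variance, correlation or effect size is given ("no sample size calculation has been performed"), so there is no planned figure to reproduce, and every size below rests on assumed values.

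**Step 1: algebra.** For respondent r in home h at time t (0 or 1), the stated model is

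y = μ + track + t·(time + track×time) + respondent type + membership + beds + u_h + v_r + e_t.

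For a respondent seen twice, whose type is unchanged,

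y_after − y_before = time + track×time + (e_1 − e_0).

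Membership, beds and both random intercepts have gone. They would remain only if the model held membership×time and beds×time.

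**Step 2: does the cancellation survive incomplete pairing?** Simulated trials used 100 homes, 25 per track, about 10 respondents per home, and SDs of 0.08 (home), 0.10 (respondent) and 0.10 (residual), with variance components held at their true values. As a check on the simulated standard error (SE) with complete pairs: the change variance is 2 × 0.10² = 0.02 with 250 respondents per track, so SE = √(0.02 × 2/250) = 0.0126, as simulated. Difference in the track-by-time estimate with and without the two main effects:

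| Respondents seen twice | Difference | SE |
|---|---|---|
| All | about 2 × 10⁻¹⁶ | 0.013 |
| 80% | largest about 0.001 | 0.013 |
| 60% | mean 0.0007 | 0.014 |
| None | mean 0.004 | 0.025 |

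**Step 3: what adjustment changes in the estimate.** In further simulated trials the allocation was balanced on both factors, and both predicted change (0.03 per SD of beds, −0.03 to +0.03 across memberships). Bias was about zero with and without the interactions. Adding them moved the estimate by 0.004 on average with complete pairs and by 0.006 with 80% paired. The empirical SD fell from 0.0136 to 0.0130 (4.4%) and from 0.0140 to 0.0133 (5.0%). When neither factor predicted change, the estimate moved by about 0.001 and nothing was gained.

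**Step 4: what adjustment changes in the reported SE.** Let τ be the between-home SD of true change, R² the share of τ² explained by membership and beds, σ the residual SD and m the respondents per home. Take complete pairs, exact balance and 25 homes per track. Then:

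- actual variance of a two-track contrast: (2/25)·[(1−R²)τ² + 2σ²/m]
- SE² of the stated model, which treats respondents' changes as independent: (2/25)·(2σ² + τ²)/m
- SE² of the stated model plus the interactions: (2/25)·[2σ² + (1−R²)τ²]/m
- SE² with a home-by-time effect but no interactions: (2/25)·[τ² + 2σ²/m]
- SE² with both: equal to the actual variance.

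Two-sided error at nominal 5% is 2·[1 − Φ(1.96 × SE/actual SD)], ignoring degrees of freedom.

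Worked case, m = 8, σ = 0.10, τ = 0.05, R² = 0.5:

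- Actual variance 0.08 × (0.00125 + 0.0025) = 0.0003, SD 0.0173.
- Stated model: 0.08 × 0.0225/8 = 0.000225, SE 0.0150; 1.96 × 0.0150/0.0173 = 1.70, error 9.0%.
- Stated model plus interactions: 0.08 × 0.02125/8 = 0.0002125, SE 0.0146 (2.8% smaller), error 9.9%.
- Home-by-time effect only: 0.08 × 0.005 = 0.0004, SE 0.0200, error 2.4%.
- Both: SE 0.0173, error 5.0%, interval 13% narrower than with the home-by-time effect alone.

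| τ | R² | Error, stated model | Error, plus interactions | Narrowing, stated model | Narrowing, home-by-time effect present |
|---|---|---|---|---|---|
| 0.03 | 0 | 8.6% | 8.6% | 0% | 0% |
| 0.03 | 0.25 | 7.5% | 7.7% | 0.5% | 3.4% |
| 0.03 | 0.5 | 6.5% | 6.8% | 1.1% | 6.9% |
| 0.05 | 0 | 14.2% | 14.2% | 0% | 0% |
| 0.05 | 0.25 | 11.6% | 12.1% | 1.4% | 6.5% |
| 0.05 | 0.5 | 9.0% | 9.9% | 2.8% | 13.4% |

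Simulation with 100 homes and 8 respondents each agrees. Error under the stated model was about 7% to 14%, and the interactions alone narrowed intervals by 0% to 3%. With a home-level error term, adjustment narrowed intervals by about 6% to 14% at R² of 0.25 to 0.5 and brought the error from 2.5% to 5.1% at R² of 0.5.

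**The case against.** The case for leaving the model alone is fair in several respects. The allocation is balanced on both factors by design, so there is no bias to remove. The protocol never says that the main effects adjust the change, and they do useful work on the least-squares means and in the baseline benchmarking. Nothing in the document shows that membership or size predicts improvement; if neither does, nothing is gained. In the logistic models the cancellation is not exact, and extra terms may not be estimable for key activities that nearly every respondent, or almost none, reports as implemented. All of this stands.

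A reader might go further and infer that the planned intervals are too wide, the test conservative and several points of power lost. The document does not support that. It would hold if the error term reflected between-home variation in change. The stated model has only home and respondent intercepts, and its SE comes from respondent-level changes. Step 4 shows the opposite tendency once homes differ in change: error above 5%, rising slightly further if the interactions are added alone.

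The objection therefore limits the size of the point and shapes the remedy. It does not remove the point: the listed covariates do not act on the effect being tested.

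**Conclusion.** The point holds as a modest one. In the linear primary model the track-by-time contrast is unadjusted for membership and beds, exactly with complete pairs and for practical purposes otherwise. There is no bias. The loss is some precision and uncorrected residual imbalance, conditional on the factors predicting change.

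Under the stated random effects, the interactions alone would narrow the reported interval by at most about 3% in the scenarios examined. The larger gain, up to about 13%, arises only where a home-by-time effect is present and the factors explain half of the between-home variation in change. These sizes assume equal tracks of 25 homes, 8 respondents per home, a residual SD of 0.10 and a home-change SD of 0.03 to 0.05, none of which the protocol gives. The cancellation itself needs none of these values. It is worth correcting because it is cheap and because no sample size calculation shows that precision is ample.

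**What to change.** In section 7.4.1, add membership × time and number of beds × time to the primary linear mixed model, keeping the main effects, together with a home-by-time random effect. The interactions and the random effect belong together: the interactions alone shrink an SE that may already be too small. Report track × time and the changes in means by track from this model, averaged over the observed distribution of membership and beds. Process-specific scores analysed by the linear model take over the same terms. For the logistic models of single key activities, add them where they can be fitted and state the simpler form to be used otherwise.

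The cost is a sentence or two of text, about four fixed-effect parameters (three for the four membership categories, one for beds) and one variance component. No new data are needed. The reported intervals may be wider than under the current model (0.0173 against 0.0150 for the SE in the worked case), because they would then reflect how much homes differ in change.

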7.4.2 Secondary objectives

Number of (psychoactive) medications used by NHRs

The number of (psychoactive) medications used by NHRs will be considered as a key secondary outcome. These data will be collected at the beginning of the intervention and after the intervention and will be collected through the monitoring tool that has been developed by VAD.

A before-after comparison of the number of (psychoactive) medications will be executed by appropriate statistical methods.

Baseline quality of the medicines' pathway and Benchmark

Using the baseline data, descriptive statistics will be reported based on the proportion of respondents that indicated a KA is performed 'Rather so' and 'Absolutely so'. Descriptives will refer to overall performance score (sum over 29 KAs), process-specific performance (sum over set of KAs) and activity-specific performance (each KA separately). For benchmarking purposes, linear and generalized linear mixed models will be used on the baseline data yielding Empirical Bayes (EB) estimates for the NH-specific levels. These EB estimates "correct" for the difference between the number of respondents per center and for differences with respect to the fixed factors included in the model (type of respondent, membership of a professional association and the number of beds available). The linear model(s) will contain a random effect of NH and the generalized linear models (fitted on multiple KAs simultaneously) will additionally include a random effect of respondent (the latter to take into account the correlation between the KAs within the same respondent).

Associations between organizational characteristics and quality of the medicines' pathway

In a set of exploratory analyses, the aforementioned (generalized) linear mixed models planned for benchmarking will be extended to determine potential associations between organizational characteristics (see Appendix 9) and the quality of the medicines' pathway in NHs.

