7 METHODOLOGY

7.1 Study design

The POOMAH study consists of a multi-arm pre-post cluster randomized controlled trial (RCT) in Flemish NHs. Nursing homes will perform a quality assessment of their medicines' pathway at baseline and will accordingly set up and monitor quality improvement initiatives. Hence, quality improvement initiatives can be expected to differ across participating NHs. A thorough process evaluation will be performed simultaneously.

Before progressing to the cluster RCT, a pilot study will be performed to assess the feasibility of executing the large-scale cluster RCT (e.g. participant recruitment, data collection, etc.).

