Next, the quality of the three processes 'storage', 'preparation' and 'administration' will be investigated using the detailed scan. This scan consists of 68 questions, to be answered on a five-point Likert Scale (see Appendix 17). This scan is also available in Limesurvey®. Only nurses and headnurses will be asked to complete this survey.

Other parts of the detailed scan can voluntarily be used by NHs to gain further insight in the quality of their medication process. The answers on these 'other parts' of the detailed scan are only for the NHs

to get more insight in these key activities, but will not be further used for data collection by the research team. In this way, these other parts of the detailed scan can be interpreted as just another tool of the toolbox.

Organizational characteristics

A survey has been developed, based on (inter)national literature and experiences from previous research projects, to map several organizational characteristics (see Appendix 4). The survey is divided into five categories, based on the System Engineering Initiative for Patient Safety (SEIPS) model: 1) persons, 2) tasks, 3) environment, 4) organization, and 5) technology and tools (20). The survey collects data on the number of residents and nurses employed at the NH (i.e. persons), on pharmacy services (i.e. tasks), on type pharmacy that delivers medication to the NH (i.e. environment), on the organization of medical pharmaceutical concertation (i.e. organization), on the types of patient files used (i.e. technology and tools), etc.

The survey on organizational characteristics will be made available in Limesurvey[®]. It will be sent to the project coordinator of each NH who will be asked to complete it.

Number of (psychoactive) drugs used by NHRs

The Flemish center of expertise in alcohol and other drugs (Vlaams expertisecentrum Alcohol en andere Drugs, VAD) provides a manual for NHs to develop a policy on the use of psychoactive medications by NHRs(21). The manual includes a monitoring tool for NHs to map the (psychotropic) medication use by NHRs, clinical outcomes (falls, hospitalizations), and the number of local interdisciplinary meetings. All data are collected on an institutional level; no data on individual residents are registered.

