In POOMAH, this monitoring tool will be used to collect data on the number of (psychoactive) drugs used by NHRs, and the number of falls and hospitalizations. By comparing the number of (psychoactive) drugs used, falls and hospitalizations at the beginning and at the end of the intervention year, the impact of the project on prescribing (e.g. changes in number of chronic (psychoactive) medications used by NHRs) can be investigated.

The local project coordinator will be asked to complete the monitoring tool (Appendix 18) in collaboration with the supplying pharmacist, according to the instructions provided in the VAD manual, in the beginning (i.e. February) and at the end (i.e. December) of the intervention year.

Demographic data

Demographic data will be collected of each NH (see 'Organizational characteristics'). Moreover, healthcare professionals participating in the NH's project team will be asked to complete a survey to collect their demographics (see Appendix 5). The same survey will be used to map demographic data

of healthcare professionals participating in interviews or focus groups (see '6.3.2 Qualitative data'). A tailored survey will collect demographics of nursing home residents and relatives participating in interviews or focus groups (see Appendix 6 and 7).

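### For the key secondary outcome the protocol states a before-after comparison with no between-track contrast, and reads the change over time as the project's impact

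*Protocol*

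**What the plan says.** Section 7.1 gives the design: "The POOMAH study consists of a multi-arm pre-post cluster randomized controlled trial (RCT) in Flemish NHs". Section 7.2 describes four tracks of support, and section 7.2.1 gives the toolbox to every NH. The primary objective in section 5 is to compare the formats and intensities of support.

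Section 7.4.2 sets the rank of the outcome: "The number of (psychoactive) medications used by NHRs will be considered as a key secondary outcome". Its analysis is one sentence: "A before-after comparison of the number of (psychoactive) medications will be executed by appropriate statistical methods". No track term, model, covariate or denominator follows.

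Section 7.3.1 says what the comparison is for: "By comparing the number of (psychoactive) drugs used, falls and hospitalizations at the beginning and at the end of the intervention year", it continues, "the impact of the project on prescribing (e.g. changes in number of chronic (psychoactive) medications used by NHRs) can be investigated". The two measurements are taken "in the beginning (i.e. February) and at the end (i.e. December) of the intervention year". On the kind of data it says: "All data are collected on an institutional level; no data on individual residents are registered".

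For the primary outcome, section 7.4.1 lists track, time and their interaction as fixed effects and names the interaction as the quantity of interest. The activity-specific and process-specific scores are expressly tied to that analysis. The medication outcome is not. Falls and hospitalisations have no analysis sentence anywhere in section 7.4.

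**The concern.** Followed as written, the analysis of the key secondary outcome compares the end of the year with its beginning and credits the difference to the project. Anything else that moved medication use, falls or hospitalisations in Flemish NHs over those ten months would be counted as effect. That includes a general trend in prescribing and the difference between a February and a December measurement. No arm goes without support, so there is no untreated trend to set against the change.

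The question that randomisation can answer is whether more intensive support changes medication use more than the toolbox does. For this outcome that question is not stated. A pooled fall in medication use could be reported as a success of the project even if the four tracks moved in parallel for reasons unrelated to any of them.

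**Working it through.** **Stated figures.** There is none to reproduce. Section 8 takes 100 NHs from a government decision and reports no sample size calculation. The documents give no SD, expected change, alpha or allocation ratio for this outcome.

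**Inputs.** From the protocol: 100 NHs, four tracks, one value per NH at each of two times. Assumed for illustration: 25 NHs per track, normally distributed NH-level changes, two-sided alpha of 0.05, no effect of any track, and a drift common to all NHs of *k* SDs of the NH-level change, with *k* from 0 to 0.5.

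**Pooled before-after test.** The mean change over 100 NHs has a standard error of 1/√100 = 0.1 SD, so the test statistic is centred at *k*/0.1 = 10*k*. The chance of a significant result is

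1 − Φ(1.96 − 10*k*) + Φ(−1.96 − 10*k*).

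- *k* = 0.1: 1 − Φ(0.96) + Φ(−2.96) = 0.170
- *k* = 0.2: 1 − Φ(−0.04) + Φ(−3.96) = 0.516
- *k* = 0.3: 1 − Φ(−1.04) + Φ(−4.96) = 0.851

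**Simulation check.** 20,000 trials per row, t-test for the before-after change, four-group F-test of change for the track contrast:

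| Drift (SD) | Pooled before-after, 100 NHs | Before-after in one track, 25 NHs | Track contrast, 4 × 25 NHs |
|---|---|---|---|
| 0 | 5.3% | 4.8% | 5.1% |
| 0.1 | 17.1% | 7.8% | 5.0% |
| 0.2 | 50.8% | 16.2% | 4.9% |
| 0.3 | 84.5% | 30.2% | 4.9% |
| 0.5 | 99.9% | 66.8% | 4.9% |

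Reporting before-after changes track by track does not solve the problem: each track's own change still carries the drift. Only the comparison between tracks removes it.

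**Price of the track contrast.** For one pair of tracks with 25 NHs each, the difference detectable with 80% power is (1.960 + 0.842) × √(2/25) = 2.802 × 0.283 = 0.79 SD of the NH-level change. Power is 42% at 0.5 SD and 81% at 0.8 SD. These figures make no correction for several pairwise comparisons.

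**The case against.** The strongest reply is that the protocol uses the same phrase with a controlled meaning. Section 7.4.1 also calls the primary analysis a before-after comparison, and there it means a model with the track-by-time interaction as its focus. Section 7.4.2 leaves the method open, and a statistical analysis plan that is not shown may fill it in. The impact sentence stands in the data-collection section and says only that impact can be investigated.

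Much of this stands. A reader might infer that an uncontrolled, pooled analysis has been decided on. The documents do not support that: nothing pools the tracks or rules out comparing them. What remains is that section 7.4.1 spells out its interaction and extends the model to other secondary scores, while the key secondary outcome gets neither. The primary model could not simply carry over, because it is built on individual respondents and these data have one value per NH. Meanwhile section 7.3.1 does attach a causal reading to the change over time. Model details can wait for an analysis plan; which contrast counts as the effect is already worded here, and worded badly.

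A second tempting inference is that changes in occupancy will distort the result. If the outcome were a raw total, a fall in occupancy from an assumed 95% to 92% would alone change it by 0.92/0.95 − 1 = −3.2%. But data at institutional level may equally be means or proportions per resident, and the monitoring tool (Appendix 18) is not shown. The occupancy effect therefore cannot be asserted; only the absence of a stated denominator can.

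It is also fair to say that the drift values are assumed, and that a track contrast cannot supply the missing untreated trend either.

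**Conclusion.** The concern holds in a limited form. For the key secondary outcome the protocol states a before-after comparison with no between-track contrast. For that outcome, falls and hospitalisations it presents the February-to-December change as evidence on the project's impact. That reading is not secure in a trial where every NH receives support. The contrast between randomised tracks is the protected comparison, and it is not named.

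The size depends on the drift, which the documents do not give. On the assumptions above, a modest common drift of 0.1 to 0.3 SD takes the false-positive rate of a pooled test from the nominal 5% to between about 17% and 85%, while a track contrast stays at about 5%. These are illustrations of a pooled test, not predictions for this trial. The primary analysis is not affected.

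**What to change.** 1. In section 7.4.2, state that the effect on the number of (psychoactive) medications, and on falls and hospitalisations, is the between-track contrast at NH level. Compare the end value by track, adjusted for the NH's own baseline value, association membership, number of beds and initial performance score, with each track set against Track 1.
2. In section 7.3.1, reword the impact sentence so that the overall change over the year is descriptive.
3. Express the outcome per resident at each time point if the monitoring tool records resident numbers, and confirm that it does. The organisational survey asks for a resident count, but the protocol does not say when or whether it is repeated, so it cannot be assumed to supply an end-of-year denominator.

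The choice of model for the contrast can be left to the analysis plan.

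The first two changes cost only wording. The third may need a resident count added at both time points if the tool lacks one. The statistical cost is real: the contrast gives relative effects between tracks, not an absolute effect of the project, and with an assumed 25 NHs per track a pairwise comparison reaches 80% power only at about 0.79 SD. The report should say so, rather than use the pooled change to fill the gap.
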